D.1.2. Spinal cord stimulator and stimulation protocol. The 2x2 Soterix® Medical transcutaneous spinal direct current stimulator model 0707-A device will be used. This is a tsDCS available only for investigational use, with which [name] has extensive experience and will provide appropriate training to the study team. This device will be appropriately labeled as an “Investigational Device. Federal (Law) limits device to investigational use”. The device will be kept in a secured area inside the LCOH Research Institute and will be made available only to trained personnel of the study team. This device allows anodal stimulation to be delivered at 2.5mA per 20-minute session or sham session consisting of short pulses (of the desired intensity) at the beginning and end of the sessions. This protocol of anodal stimulation has been reported to be effective in inhibiting ascending pathways with a lasting effect, to be safe and well under the threshold for tissue damage (77, 79). If stimulation intensity (in active or sham protocols) is not tolerable at 2.5mA, the clinician may decide to decrease intensity to 2.0 mA or 1.5 mA. If 1.5 mA stimulation intensity is not tolerated, the subject may be withdrawn from the study. If subject has tolerated a stimulation intensity of less than 2.5mA, the study clinician may attempt to increase the dose to 2.0mA or 2.5mA when considered clinically appropriate. An anode electrode (5x10cm) will be placed at the level of the 10th vertebrae spinal process. At this level, the current is expected to spread longitudinally through the spinal cord up to three additional vertebral levels (96). The cathode (5x7cm) electrode will be placed on the right shoulder over the deltoid area (78, 79, 97). Participants will be scheduled to receive sham or active tsDCS sessions three times/week. Subjects will be randomized in a 1:1 ratio using a simple allocation method to one of two experimental groups: 1) sham or 2) stimulation protocol. Randomization will be double-blinded. An independent operator (trained personnel from the research team) will prepare the tsDCS device parameters for each session, but will not participate in the rest of the assessments. Patients and raters will remain blinded to SCS protocol assigned to each participant throughout the study. During the session, subjects will remain in a calm and relaxing environment. All participants will be scheduled for the same procedures and number of scheduled visits during the eight-week follow-up period. (**Table 2**)

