Primary Outcome: Difference in change from baseline to week 8 (or last available observation) in MADRS scores between active and sham tsDCS groups. **Secondary Outcome:** **a)** differences in AE's frequency between active and sham tsDCS groups, **b)** association between change from baseline to week 8 (or last available observation) in MADRS scores, and clinical (CGI-I, CGI-S, PHQ-9, MAIA, BES and 4DSQ), autonomic (BP, HR) and metabolic (anthropometric, adiponectin, leptin, cortisol, FGF-21 and LCn-3) parameter change from baseline to week 8(or last available observation), and **c)** MADRS sub-component (98) scores, clinical parameters (CGI-I, CGI-S, PHQ-9, MAIA, BES and 4DSQ), autonomic (BP, HR), and metabolic (anthropometric, adiponectin, leptin, cortisol, insulin, FGF-21 and LCn-3) parameters change from baseline to week 8 (or last available observation) difference between Active and Sham tsDCS groups. **Exploratory outcome measures:** **a)** difference in change from baseline to week 8 (or last available observation) in offline ERT and Stop signal task scores between active and sham tsDCS groups; and **b)** difference in change from baseline to week 8 (or last available observation) in offline and online change ERT and stop signal task scores between active and sham tsDCS groups

F. SAFETY MEASURES

Potential Risks. Safety evaluation will consist in recording all laboratory tests, vital signs and ECG results, suicidality monitoring (each SCS session), physical and neurological examinations and any adverse events (AE). As mentioned above, literature suggests that current density below 25 mA/cm² induces no tissue damage (99). Findings will be recorded as AEs at the discretion of the investigator. Known side effects to tsDCS are paresthesia, redness, itch, or pain in stimulated area. If they occur, these side effects tend to disappear within minutes to hours after stimulation. To our knowledge, no serious adverse effects have been reported with the use of transcutaneous direct current stimulation protocols using 2.5mA/cm² (100).

Risk/Benefit Assessment. Participants will be informed that there are other FDA approved treatment alternatives for major depressive disorder and that their participation in this study is voluntary. Therapeutic options include antidepressant medications, psychotherapy, invasive and non-invasive neuromodulation tools. Participants will also be

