
outcome and clinical trials studies. A study physician will work with the patient to arrange admission in the event that it is determined that a study participant needs psychiatric or medical hospitalization.

G. SAMPLE SIZE.

This is an exploratory pilot clinical trial for which up to 60 (including screen fails) participants will be screened in an effort to recruit 20 participants that will receive either sham (n=10) or active treatment (n=10) for 8 weeks. Recruitment efforts will be aimed at a 2 patient/month rate. The exploratory nature of the study precludes a sample size that would enable detection of small but still clinically relevant effects at conventional significance thresholds. However, estimates of effect sizes with confidence intervals will be useful as inputs to larger confirmatory studies if these effects fall in an appropriate range (i.e., at least moderate sample effect sizes of approximately 0.50 standard deviations), even if the conventional significance is not achieved.

H. FEASIBILITY OF RECRUITMENT AND RETENTION

Resources and Infrastructure: The University of Cincinnati (UC) College of Medicine, Department of Psychiatry was founded in 1932 and UC is the 14th largest recipient of NIH funding. Among departments of Psychiatry, UC has one of the largest psychopharmacology research programs in the United States dedicated to depression and bipolar disorder. The faculty has a long-term successful record of sustained research support related to mood, eating, and impulse control disorders and pharmacological treatments.

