Data management and analyses will be organized and performed by the research team under the guidance of [name], Director of the Division of Biostatistics in the Department of Psychiatry at the University of Cincinnati, who has participated in the development of this analytic plan. Data will be collected via Case Report Forms. The research coordinator will be responsible for managing the study flow, maintaining case report forms, and entry data into a password-protected database on REDcap.

Data Analysis. *Specific Aim 1: Prediction 1)* Active tsDCS treatment will result in a greater decrease in depressive symptom severity (MADRS) compared to Sham in adult patients diagnosed with MDD. *Efficacy:* Longitudinal effect of tsDCS will be assessed by comparing change in MADRS scores from baseline to week 8 (or last available observation). To take maximum advantage of intermediate observations while avoiding assumptions about the trajectory of change over time, we will use a repeated-measures ANOVA model (i.e., with time as a categorical variable), and the primary hypothesis test will be a planned contrast of the baseline-week 8 differences between groups. *Prediction 2)* Active tsDCS is safe and well tolerated in adult patients diagnosed with MDD. *Safety:* A similar analysis as used for efficacy data will be performed for laboratory assays, vital signs, anthropometric, clinical, autonomic and metabolic variables. Frequencies of AE's will be compared between groups using comparative analysis. *Specific Aim 2: Prediction 3)* Baseline and change in interoceptive awareness,

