somatic symptoms, clinical, autonomic and metabolic parameters will be associated with change in depressive symptom severity. A correlation analysis will be used to evaluate the association between treatment and depressive symptom severity, both total and in components (items). Correlation analysis will also be performed by gender, autonomic and metabolic parameters. Prediction 4) Active tsDCS treatment will result in a greater change in interoceptive awareness, anxiety and somatic symptoms, clinical, autonomic and metabolic parameters. Longitudinal effect of tsDCS will be assessed by comparing MADRS sub-component scores, clinical parameters (CGI-I, CGI-S, PHQ-9, BES, MAIA, and 4DSQ), autonomic, and metabolic parameters change from baseline to week 8 (or last available observation) difference between Active and Sham groups using a repeated-measures ANOVA as described above. Throughout, tests and confidence intervals for effect sizes will be two-sided, $\alpha=0.05$.

J. PROTECTION OF HUMAN SUBJECTS.

The data and safety monitoring plan for the proposed study will include monitoring of efficacy data by an independent Data Safety Monitoring Board (DSMB) and monitoring of tolerability data, including adverse events and serious adverse events, by the study investigators as well as the independent DSMB and the University of Cincinnati College of Medicine Institutional Review Board (IRB). The DSMB will consist of non-study related faculty with relevant research experience.

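### The only stated analysis of continuous safety variables is the efficacy mean contrast, which is unlikely to show an extreme laboratory change in one to three of ten patients; a by-arm patient count and listing should be added

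*Combined protocol and SAP*

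**What the plan says.** Section I (Data Analysis, Specific Aim 1, Prediction 2) sets the safety analysis: "A similar analysis as used for efficacy data will be performed for laboratory assays, vital signs, anthropometric, clinical, autonomic and metabolic variables". The efficacy analysis it refers to is a repeated-measures ANOVA with categorical time, tested by a planned contrast of the baseline-to-week-8 differences between arms. The next sentence adds a comparison of adverse-event frequencies, without naming a test.

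The route from an abnormal value to an adverse event is described in two places. Section J has the clinical team review every subject's laboratory and safety measures after each visit, and its adverse-event definition covers clinically significant clinical or laboratory change. Section F says: "Findings will be recorded as AEs at the discretion of the investigator". Neither gives numeric limits. No shift table, abnormal-value count or listing is planned. ECG is a safety measure in Section F, but Section I names no analysis for it.

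The same contrast appears under Specific Aim 2, Prediction 4: "Active tsDCS treatment will result in a greater change in interoceptive awareness, anxiety and somatic symptoms, clinical, autonomic and metabolic parameters". Section A words that prediction as a greater decrease. Section E lists the variables, which include blood pressure, heart rate, anthropometric measures and the metabolic markers.

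**The concern.** Harm from a device in a small trial often appears as a large change in a few patients, not as a shift of the whole arm. A contrast of means handles that pattern poorly, because the few extreme values inflate the standard error along with the mean difference. With about ten patients per arm, one or two striking laboratory abnormalities could leave the planned statistic unremarkable.

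Two features add to this. The contrast compares baseline with week 8, whereas blood pressure and heart rate are taken before and after every session (Sections D.1.4 and D.2). A mid-trial excursion that has resolved by week 8 does not enter the estimate. Also, for the variables shared with Prediction 4, a larger fall on active is the hoped-for effect under one prediction and a difference from sham under the other. The plan gives no rule for telling a harmful change from an intended one.

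At stake is how informative the safety report will be in a pilot that is meant to support a larger trial.

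**Working it through.** The documents state no safety power, margin or threshold, so there is no figure of theirs to reproduce.

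**Inputs**
- Arm size: "recruit 20 participants that will receive either sham (n=10) or active treatment (n=10) for 8 weeks" (Section G). This is nominal, since "Subjects will be randomized in a 1:1 ratio using a simple allocation method" (Section D.1.2).
- Level: 0.05, where "tests and confidence intervals for effect sizes will be two-sided" (Section I).
- Time points: general safety laboratory tests 2 (visits 0 and 6); metabolic markers 3 (visits 1, 4 and 6) (Section D.1.3); anthropometric measures 6 (Section D.1.5).
- SD of change: not given. Shifts are in SD units over an assumed range of 2 to 20.
- ANOVA error term: not stated. Two readings are shown below.

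**Two time points.** The contrast equals a two-sample t on change, with 18 df. Let k of 10 active patients change by D and everyone else by 0.
- Mean difference = kD/10.
- Active-arm variance = D² × (k/10)(1 − k/10)(10/9); sham variance = 0.
- Standard error = √(active-arm variance/10).
- D cancels, so t = 3√(k/(10 − k)).

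| k of 10 | limiting t | p |
|---|---|---|
| 1 | 1.00 | 0.33 |
| 2 | 1.50 | 0.15 |
| 3 | 1.96 | 0.065 |
| 4 | 2.45 | 0.025 |

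The critical value is 2.101, so four patients are needed in the limit.

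With normal noise (SD of change 1; 100,000 runs; equal-variance t), the percentage of trials with p < 0.05 is:

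| k | 2 SD | 3 SD | 5 SD | 10 SD | 20 SD |
|---|---|---|---|---|---|
| 1 | 4.9 | 4.5 | 3.4 | 0.4 | 0.0 |
| 2 | 7.9 | 9.2 | 8.4 | 2.8 | 0.0 |
| 3 | 13.8 | 18.6 | 24.1 | 24.8 | 16.6 |
| 4 | 23.5 | 35.6 | 54.5 | 81.8 | 98.5 |

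One affected patient in ten is flagged no more often than chance alone would flag the test.

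**More time points, pooled error.** With T time points, the shift at the last one, and one pooled within-patient error term, t = √(4.5 T p/(1 − p)), where p = k/10 and df = 18(T − 1). At T = 2 this returns the formula above.

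| T | critical t | k = 1 | k = 2 | k = 3 |
|---|---|---|---|---|
| 3 | 2.028 | 1.22 | 1.84 | 2.41 |
| 6 | 1.987 | 1.73 | 2.60 | 3.40 |
| 7 | 1.982 | 1.87 | 2.81 | 3.67 |

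At T = 3 with independent errors (40,000 runs), 3 of 10 is detected in 28% of trials at 3 SD, 75% at 10 SD and 97% at 20 SD. For 2 of 10, detection is 14 to 21% over 3 to 20 SD. One of 10 never reaches the critical value in the limit. If each contrast instead uses its own change-score error, the two-time-point results apply to every variable.

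**What a count would show.** Exact 95% intervals: 0/10 = 0 to 30.8%; 1/10 = 0.3 to 44.5%; 2/10 = 2.5 to 55.6%; 3/10 = 6.7 to 65.2%. Two-sided Fisher p for 1 to 5 of 10 against 0 of 10: 1.00, 0.47, 0.21, 0.087, 0.033.

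**The case against.** The strongest reply is that the plan already has a patient-level route. Laboratory and safety measures are reviewed after each visit, clinically significant changes fall under the adverse-event definition, adverse-event frequency by arm is a secondary outcome (Section E), and an independent monitoring board reviews events. A reader might infer that safety is judged by the mean contrast alone; these provisions show that it is not. What remains is that entry to this route depends on discretion without preset limits, so an abnormal value that is not called an event appears only in a mean, and an ECG value in no stated analysis.

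A reader might also infer that the contrast cannot flag three patients in ten. That is too strong. Even with two time points it does so in 14 to 25% of trials over the assumed shifts. With three or more time points and pooled error, large shifts are likely to be found.

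Nor does any section say that a null contrast proves safety or that an arm difference disproves it. One variable can inform both mechanism and safety. The overlap with Prediction 4 also leaves out the general safety laboratory tests (blood count, electrolytes, liver, kidney, lipids, glucose, TSH), which are not in its outcome lists. Reading the overlap as benefit fits Section A's greater decrease; Section I says only greater change.

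Finally, a count is no better as a significance test: Fisher needs 5/10 against 0/10, where the two-time-point contrast needs four patients in the limit. And a modest shift across the whole active arm, with nobody crossing a limit, shows in means and not in counts. Both points stand. They are reasons to add the count as description and not to drop the contrast.

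**Conclusion.** The point holds as a reporting gap that is cheap to close. The mean contrast is the only stated analysis of continuous safety variables. For the two-time-point safety laboratory tests it is unlikely to show an extreme change in one to three of ten active patients: detection is 0 to 4.9%, 0 to 9.2% and 14 to 25% respectively. For variables with more time points it is less blind if a pooled error term is used, which the plan does not specify. At any number of time points it leaves out excursions that resolve before week 8.

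These figures assume ten per arm, normal noise, equal shifts among affected patients, no change in the others, and shifts of 2 to 20 SD. The documents give no SD to narrow that range.

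For blood pressure, heart rate, anthropometric and metabolic variables, neither a significant nor a non-significant mean difference should by itself be read as showing harm or safety. The documents do not support the stronger conclusions that abnormal values go unexamined or that the means carry no safety information.

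**What to change.** Keep the repeated-measures contrast and add to the Prediction 2 analysis:

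- A count by arm of patients with any post-baseline laboratory, blood-pressure, heart-rate or ECG value outside limits that the clinical team fixes before unblinding.
- Exact 95% confidence intervals for each proportion, using actual arm sizes. With none in ten the interval still runs to 30.8%, which guards against reading an empty cell as proof of safety.
- A listing of each such patient, with the value and visit.
- One sentence saying that the table is descriptive and not a significance test, and that a mean difference in the variables shared with Prediction 4 does not by itself establish safety or harm.

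The cost is SAP wording, one extra table with its listing, and agreeing the limits in advance. The data are already collected; no visits or patients are added. One caution: 24 sessions with readings before and after give up to 48 blood-pressure and heart-rate readings per patient, so some chance excursions should be expected in both arms. The sham column is needed to interpret the active one.

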Major depressive disorder (MDD) is a recurrent and chronic mood disorder that affects 14% of the adult population during their lifetime. Current treatment options are partially effective and the neurobiology of MDD is largely unknown. Recent evidence points to an important role of brain-body communication in the integration of mood and therefore in depression. Information travelling from the body to the brain through the dorsal horns in the spinal cord is essential to provide consciousness of emotional experience in a process called interoceptive awareness. This information is then used by the brain to adjust bodily function through hypothalamic and autonomic outputs. Increased sympathetic activity and somatic symptoms have been documented in MDD and suggest disturbed brain-body communication. Spinal cord stimulation (SCS) has been used in the past to decrease sympathetic activity and modulate spinal input to the brain. Indirect evidence suggests that SCS might have antidepressant effects. Transcutaneous spinal direct current stimulation(tsDCS) devices represent an effective, non-invasive, low cost alternative to surgically implanted SCS devices. We believe that extant data support our overarching HYPOTHESIS that an altered sensory input to the brain through the dorsal horns of the spinal cord contributes to the pathophysiology of depressive symptoms and that tsDCS will be effective and safe in treating MDD by decreasing sympathetic activity and restoring metabolic function. Thus, we aim to 1) determine the efficacy and safety of tsDCS in adult patients with MDD and 2) investigate interoceptive awareness, somatic symptoms, autonomic and metabolic regulation as potential mediators of antidepressant response to tsDCS. We predict that 1) Active tsDCS treatment will result in a greater decrease in depressive symptom severity compared to Sham tsDCS in adult patients with MDD, 2) active tsDCS will be safe and well tolerated in adult patients with MDD and 3) change in interoceptive awareness, somatic symptoms, and autonomic and metabolic parameters will be associated with change in depressive symptom severity. To accomplish these aims, we will conduct an 8-week, double blinded, randomized, sham controlled, parallel group, pilot clinical trial study design. A total of 20 adult antidepressant-free MDD patients will be randomized to receive Active (n=10) or Sham (n=10) tsDCS protocols for 8 weeks in a 1:1 ratio. As an initial test of our hypothesis, we will combine the use of a tsDCS device, psychometric instruments to diagnose MDD (M.I.N.I.), and measures of depressive symptom severity (MADRS and PHQ-9), somatic symptoms (4DSQ), interoceptive awareness (MAIA), autonomic function (blood pressure, heart rate), and potential metabolic markers (cortisol, LCn-3 fatty acids, adiponectin, leptin, insulin and fibroblast growth factor-21) known to be regulated by sympathetic activity as predictors of response. This will be the first pilot study to evaluate the potential antidepressant effects of tsDCS in adult patients diagnosed with MDD. It is anticipated that the results of this pilot clinical trial will provide preliminary data in support of a larger future trial that will additionally incorporate neuroimaging to investigate central mechanisms.

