Specific Aim 2: To investigate interoceptive awareness, anxiety and somatic symptoms, autonomic and metabolic regulation as potential mediators of antidepressant response to tsDCS. Prediction 3: Change in interoceptive awareness, somatic symptoms, and autonomic and metabolic parameters will be associated with change in depressive symptom severity. Prediction 4: Active tsDCS treatment will result in a greater decrease in depressive symptom sub-components, interoceptive awareness, anxiety and somatic symptoms, autonomic and metabolic parameters.

To accomplish these aims, we will randomize 20 adult antidepressant-free MDD patients to active (n=10) or sham (n=10) tsDCS protocols for 8 weeks in a double blind 1:1 ratio. We will evaluate clinical, autonomic, and metabolic variables that may be involved in the proposed mechanism as possible mediators of antidepressant response. This will be the first 8-week, double blinded, randomized, sham controlled, parallel group pilot clinical trial to evaluate the efficacy and safety of tsDCS in adult patients with MDD. It is anticipated that the results of this pilot trial will provide preliminary data in support of a larger future trial that will additionally incorporate neuroimaging to investigate central mechanisms.

B. BACKGROUND AND SIGNIFICANCE:

B.1 Public Health Significance:

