Visit 0 (Screening). Subjects will be informed about study procedures and given a written informed consent to sign voluntarily before any study procedure is initiated (See Informed consent form attached to this protocol). Then, the clinical staff will evaluate the participant in order to obtain a psychiatric and medical history. The MINI will be used to confirm MDD diagnosis, the MADRS to evaluate depressive symptom severity and the CSSRS for suicidality. The clinical research team will perform a full neurological and physical evaluation, ECG, cardiovascular measurements, laboratory tests, urinalysis, urine drug test, and a blood pregnancy test (if applicable). After eligibility is confirmed, a baseline visit will be scheduled.

Visit 1 (Baseline). After verification of eligibility, subjects will be randomized to an “active” or to a “sham” tsDCS protocol. Treatment allocation will remain double-blinded throughout the study to raters and study physicians. A MADRS, CGI-S, CSSRS, PHQ-9, 4DSQ, BES and MAIA will be completed. BMI, waist and abdominal circumference, vital signs, blood sample and ECG will be obtained. A physical and neurological evaluation will be conducted. Participants will complete the ERT and SST prior and during the SCS protocol. Each participant will receive the assigned SCS protocol.

SCS sessions (1-24): Three tsDCS sessions per week will be scheduled. A CSSRS will be completed before each SCS session. Blood pressure and heart rate will be evaluated prior and after each tsDCS session. AE's will be assessed after each session through open-ended questions.

Full visits 2, 3, 4, and 5: A MADRS, CSSRS, CGI-S, CGI-I, PHQ-9, 4DSQ, BES and MAIA scales will be completed.

Anthropometric measures (Visit 3, 4, 5), vital signs, and ECG (Visit 4) will be obtained. A blood sample (visit 4), urine drug test (Visit 4) and pregnancy test will be performed if applicable (visit 4). A physical and neurological evaluation will be

conducted (Visit 3, 4, and 6). Participants will complete the ERT and SST prior and during the SCS protocol (Visit 4). Each participant will receive the respective tsDCS protocol. AE's will be recorded after each tsDCS session.

Full Visit 6 (Final visit): A MADRS, CSSRS, CGI-S, CGI-I, PHQ-9, 4DSQ, BES and MAIA scales will be completed.

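### Section I relates baseline parameters to MADRS change with no stated term for Visit 1 MADRS or arm, so the result can be distorted and cannot show response to tsDCS

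*Combined protocol and SAP*

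**What the plan says.** Section I (Data Analysis, Specific Aim 2, Prediction 3) states the prediction as "Baseline and change in interoceptive awareness", continuing with "somatic symptoms, clinical, autonomic and metabolic parameters will be associated with change in depressive symptom severity". Both the starting value and the change of each parameter are therefore candidate correlates.

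The method follows: "A correlation analysis will be used to evaluate the association between treatment and depressive symptom severity, both total and in components (items"). A further sentence adds correlation analyses by gender and by autonomic and metabolic parameters. Neither sentence mentions Visit 1 MADRS or arm as a covariate, and neither says which pairs of variables are to be correlated.

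The other statements of the same prediction are narrower. Section A words it as "Change in interoceptive awareness, somatic symptoms, and autonomic and metabolic parameters will be associated with change in depressive symptom severity". Section E, secondary outcome (b), is the "association between change from baseline to week 8 (or last available observation) in MADRS scores, and clinical", autonomic and metabolic "parameter change from baseline to week 8(or last available observation"). Both concern change with change. The abstract describes the metabolic markers as "known to be regulated by sympathetic activity as predictors of response".

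On timing, Section D.2 says of Visit 1: "A MADRS, CGI-S, CSSRS, PHQ-9, 4DSQ, BES and MAIA will be completed". The clinical scales are thus recorded on the same occasion as the MADRS score that is later subtracted.

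**The concern.** MADRS change is the week-8 (or last available) score minus the Visit 1 score. Suppose a baseline parameter moves with the Visit 1 MADRS because it measures similar content or was recorded on the same day. It can then correlate with change through the subtracted score, even if it says nothing about week 8 beyond what Visit 1 MADRS already says. PHQ-9, CGI-S and 4DSQ are the most exposed.

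There is a second problem. Aim 2 concerns mediators of antidepressant response to tsDCS, but half the participants receive sham. A correlation pooled over arms describes who improves, not who improves because of stimulation.

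What is at stake is the choice of markers for the larger trial that this pilot is meant to inform. Some could be favoured because they overlap with baseline severity, or because they are prognostic under either treatment.

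**Working it through.** The plan gives no correlation, SD or power figure for Prediction 3, so there is no figure to reproduce.

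**Inputs from the documents.** N=20, 10 per arm (Section G); two-sided alpha 0.05 (Section I); entry MADRS 20 to 35 (Section D.1). If scores were uniform over that range, the SD would be 15/√12 = 4.3.

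**Assumptions.** Visit-to-visit MADRS correlation rho of 0.3 to 0.5; correlation rx of 0.5 to 0.7 between the parameter X and Visit 1 MADRS; week-8 SD s8 either equal to the Visit 1 SD s1, or 6 to 9 against s1 = 4.3. X is taken to carry no information on week 8 beyond Visit 1 MADRS.

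**Formula.** corr(X, change) = rx × k, where k = (rho·s8 − s1) / √(s1² + s8² − 2·rho·s1·s8).

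**Values of k.**
- Equal SDs: k = −√((1 − rho)/2), which is −0.59 at rho 0.3 and −0.50 at rho 0.5.
- 4.3 versus 6, rho 0.3: (1.8 − 4.3)/√39.01 = −0.40. At rho 0.5: (3.0 − 4.3)/√28.69 = −0.24.
- 4.3 versus 9, rho 0.3: (2.7 − 4.3)/√76.27 = −0.18. At rho 0.5: (4.5 − 4.3)/√60.79 = +0.03.

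**Spurious r and rejection rate** (n=20, critical |r| = 0.444, 40,000 simulated trials per setting):

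| SDs, Visit 1 vs week 8 | rho | rx × k, rx 0.5–0.7 | Unadjusted test rejects |
|---|---|---|---|
| equal | 0.3–0.5 | −0.25 to −0.41 | 19%–46% |
| 4.3 vs 6 | 0.3–0.5 | −0.12 to −0.28 | 8%–23% |
| 4.3 vs 9 | 0.3–0.5 | −0.13 to +0.02 | 5%–8% |
| 4.3 vs 9 | 0.7 | +0.15 to +0.21 | 9%–14% |

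The distortion is negative when rho·s8 < s1, zero when rho·s8 = s1 (for example s1 = 4, s8 = 8, rho = 0.5) and positive beyond that. With rx = 0.3, equal SDs and rho = 0.5, it is −0.15 and the test rejects in 9.6% of trials.

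**Does adjusting for Visit 1 MADRS settle it?** Under this data model, yes: the partial correlation given Visit 1 MADRS rejects in 4.7% to 5.3% of trials. Under a different model, no. If X tracks only stable true severity, equally related to both MADRS scores, the unadjusted correlation with change averages 0.00 and rejects in about 5%. The adjusted one rejects in 17% to 48% in the settings tried, because Visit 1 MADRS measures true severity with error and X picks up the remainder.

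**Pooling the arms.** Let the slope of change on X be b_s in sham and b_a in active. With equal arms and similar spread of X, the pooled slope is about (b_s + b_a)/2. Pure prognosis (b_s = b_a = b) and pure response to stimulation (b_s = 0, b_a = 2b) both give b. The pooled analysis cannot tell them apart; the difference b_a − b_s can. Coupling through the Visit 1 score that is common to both randomised arms cancels in that difference.

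**The case against.** **The plan does not commit to an unadjusted correlation.** Its operative sentence speaks of treatment and symptom severity, so the fault could be called under-specification. That stands in part: the text does not choose a wrong analysis explicitly. But it names correlation as the only method and gives no covariate, and the pairs still have to be specified.

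**The size is assumption-driven.** This stands. A reader might infer that any parameter tied to baseline severity will appear to predict response. The documents do not support that. Entry is restricted to MADRS 20 to 35 while week 8 is unrestricted, so the week-8 SD may well be the larger, and the distortion may then be small, nil or reversed. The restriction is not a complete defence, because Section D.2 takes a screening MADRS at Visit 0 and another at Visit 1 and does not say that the range is reapplied at Visit 1. The documents also give no correlation between MADRS and the metabolic markers, to which the abstract's predictor language most directly attaches; 0.5 to 0.7 is more natural for overlapping depression scales.

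**Association with change is all that is predicted.** If severity is related to change, then a marker of severity is too, and finding that is no error for the literal prediction. This is fair, but it does not license calling the marker a predictor of response.

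**It matters little.** This is a secondary analysis in an exploratory pilot, and no rule carries these correlates into the next trial. Both statements are correct. They limit the priority, not the case for a small change in wording.

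**Conclusion.** The concern holds in limited form. The baseline correlates appear only in Section I, with no matching outcome in Section E and no stated term for Visit 1 MADRS or arm. For parameters close to the Visit 1 MADRS, the spurious correlation lies between about −0.41 and +0.02 and the rejection rate between about 5% and 46%, for rho 0.3 to 0.5, rx 0.5 to 0.7 and the assumed SDs. The upper end needs equal SDs, rho 0.3 and rx 0.7 together; at rho 0.7 the sign can reverse.

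A reader might also infer that baseline adjustment alone cures the problem. It does not when the parameter reflects stable severity and Visit 1 MADRS carries measurement error.

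The firmer conclusion does not depend on the SDs: a correlation pooled over active and sham cannot identify predictors of response to tsDCS. The change is worth making as a low-cost improvement. The primary MADRS contrast is unaffected.

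**What to change.** For baseline parameters, fit week-8 (or last available) MADRS on Visit 1 MADRS, arm, the parameter and arm-by-parameter, with arm coded −½ and +½ so that the parameter main effect is an average over arms.

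- Report the main effect as prognostic only. Note that it may still reflect stable severity because Visit 1 MADRS is measured with error, and show the unadjusted correlation beside it.
- Call a parameter a predictor of response to tsDCS only on the arm-by-parameter estimate with its CI.
- State in Section I which pairs the correlation analyses cover.
- List the baseline analysis in Section E and align Section A, or delete *Baseline and* from Prediction 3 in Section I, so that the three sections agree.

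The cost is a few lines of text and two or three degrees of freedom per model: two for Visit 1 MADRS and arm, a third for the interaction. With 10 per arm the interaction interval will be wide. Its standard error is at least about √(1/9 + 1/9) = 0.47 residual SDs per SD of the parameter. That imprecision should be reported as such, which suits the estimation purpose set out in Section G.
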